- h. Any subjects with observed QTcF prolongation of potential significance should have the ECG repeated for confirmation and electrolytes assessed and replaced as needed prior to action with study drug being taken. An average of QTcF values from triplicate ECGs and NOT an individual QTcF value from a single ECG should be used for dose modification considerations.

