Abnormal laboratory values should not be listed as separate AEs if they are considered to be part of the clinical syndrome that is being reported as an AE. It is the responsibility of the investigator to review all laboratory findings in all subjects and determine if they constitute an AE. Medical and scientific judgment should be exercised in deciding whether an isolated laboratory abnormality should be classified as an AE. Any laboratory abnormality considered to constitute an AE should be reported on the Adverse Event eCRF.

Abnormal ECG (QTcF) results, if not otherwise considered part of a clinical symptom that is being reported as an AE, should be considered an AE if the average QTcF interval is ≥ 450 ms or there is an average increase of more than 60 ms from baseline (defined as average QTcF value from C1D1 pre-dose ECGs). Any ECG abnormality that the investigator considers as an AE should be reported as such.

Death should be considered an outcome and not a distinct event. The event or condition that caused or contributed to the fatal outcome should be recorded as the single medical concept on the Adverse Event eCRF. Generally, only one such event should be reported. If the cause of death is unknown and cannot be ascertained at the time of reporting, "unexplained death" should be recorded on the Adverse Event eCRF. If the cause of death later becomes available (e.g., after autopsy), "unexplained death" should be replaced by the established cause of death.

All AEs observed during the study will be reported on the eCRF. All AEs, SAEs, and other reportable safety events that occur after the consent form is signed must be reported by the investigator. Other events that occur prior to the consent form is signed should be recorded as medical history.

All AEs or events of clinical interest (ECIs) that occur after the consent form is signed through 30 days following cessation of study treatment must be reported on the eCRF by the investigator. See Section [9.2.2](#) for further discussion of SAEs and ECIs.

All AEs must be recorded and followed through 30 days following cessation of study treatment (or 30 days after final dose if the subject initiates new anticancer therapy), or until resolution, whichever comes first.

Every effort must be made by the investigator to categorize each AE according to its severity and its relationship to the study treatment.

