2. An elevated AST or ALT value that is ≥ 3 times the upper limit of normal (\times ULN) and an elevated total bilirubin value that is $\geq 2 \times$ ULN and, at the same time, an alkaline phosphatase value that is $< 2 \times$ ULN, as determined by protocol-specified laboratory testing or unscheduled laboratory testing.*

**Note: These criteria are based upon available regulatory guidance documents. The purpose of the criteria is to specify a threshold of abnormal hepatic tests that may require an additional evaluation for an underlying etiology. The study site guidance for assessment and follow up of these criteria can be made available. It may also be appropriate to conduct additional evaluation for an underlying etiology in the setting of abnormalities of liver blood tests including AST, ALT, bilirubin, and alkaline phosphatase that do not meet the criteria noted above. In these cases, the decision to proceed with additional evaluation will be made through consultation between the study investigators and the Sponsor or medical monitor. However, abnormalities of liver blood test values that do not meet the criteria noted above are not ECIs for this study.*

3. QTcF interval ≥ 450 ms or a > 60 ms increase from baseline (defined as average QTcF value from C1D1 pre-dose ECGs).
4. Significant GI toxicity, e.g., nausea, vomiting, diarrhea, or constipation not easily managed with symptomatic medications in an outpatient setting.

In addition to the above ECIs, Events Associated with Special Situations include pregnancy or exposure to study treatment through breastfeeding; AEs associated with study treatment overdose, or medication error. Events associated with special situations and ECIs are to be captured using the SAE procedures but are to be considered as SAEs only if they meet one of the above criteria. All ECIs and AEs associated with special situations are to be reported on a completed SAE form by email or fax whether or not they meet the criteria for SAEs, and are subject to the same reporting timelines described in Section **10.1.1**.

Serious adverse events must be reported after the consent form is signed through 90 days following cessation of study treatment, or 30 days after final dose if the subject initiates new anticancer therapy, whichever occurs first.

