- **Categorical variables**: Descriptive statistics will include counts and percentages per category. The denominator in all percentage calculations will be the number of participants in the relevant analysis population with non-missing data, unless specifically stated otherwise. Percentages will be displayed to one decimal place. Proportions will be displayed to 3 decimal places.

95% Confidence Intervals (CIs) will be displayed to two decimal place for percentages. Proportions will be displayed to 3 decimal places. P-values will be displayed to 3 decimal places.

- **Time to Event Analysis**: Through the Kaplan-Meier (KM) method, nonparametric estimates of the survivor function will be represented by quartile estimates (Q1, Median and Q3) along with 95 CIs. Product limit estimates will be presented as part of appendices to the study outputs (SAS output).

KM plots of estimated survival/failure curves will be produced by cohort.

- **Repeat/unscheduled assessments**: Only values collected at scheduled study visits/time points will be presented in summary tables. If a repeat assessment was performed, the result from the original assessment will be presented as the result at the specific visit/time point. All collected data will be included in the data listings.

- Assessment windows: All assessments will be included in the data listings and no visit windows will be applied to exclude assessments that were performed outside of the protocol specified procedure windows.
- Result display convention: Results will be center aligned in all summary tables and listings. Subject identifiers visit and parameter labels may be left-aligned if required.
- Date and time display conventions: The following display conventions will be applied in all outputs where dates and/or times are displayed:

Date only: YYYY-MM-DD

Date and time: YYYY-MM-DD HH:MM

If only partial information is available, unknown components of the date or time will be presented as 'NK' (not known), i.e., '2016-NK-NK'. Times will be reported in military time.

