#### Thyroid Function:

- Triiodothyronine (T3)
- Free triiodothyronine (FT3)
- Free Thyroxine (FT4)
- Thyroid-Stimulating Hormone (TSH)

All laboratory data collected at scheduled and unscheduled visits will be included in the listings, but only results collected as scheduled visits will be included in the summary tables.

Results for individual parameters may be reported in different units depending on the analyzing laboratory. The results (and the corresponding normal range cut-off values) for individual parameters will be converted to International System of Units (S.I.) units to summarize the data.

For all the parameters where a unit value has been reported, the parameter names that will be used in the outputs will comprise of the test name and the unit of measure, for example, 'Albumin (g/L)'. For the urinalysis parameters, the parameter name will be the reported test name only. Parameters will be sorted alphabetically within tables and listings.

For all parameters where a normal range limit value was reported, the normal range will be derived based on the available lower and upper limit values and any reported mathematical symbols. If both a lower and upper limit value is available, the normal range will be presented as '(Lower, Upper)'.

The hematology, serum chemistry, coagulation, urinalysis analyses & microscopic urinalysis, and thyroid function results tables will present summary statistics for each laboratory parameter within the specific test panel. For each parameter, summaries will be presented for the baseline and each scheduled post-baseline visit. In addition, summaries will be presented for the change from baseline values at each scheduled post-baseline visit (continuous descriptive analysis).

The decimal precision to which the summaries for each parameter will be based on the maximum number of decimals to which the reported result or the normal range limits are presented to in the raw data. The results and normal ranges will be displayed to the same decimal precision in the listings.

A cross-tabulation of the worst grade that observed in planned and unplanned visits until ED/EOT versus the baseline grade will be presented with shift table for both of the NCI-CTCAE grade and investigator's clinical significance abnormality assessment.

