### **13.4 12-Lead Electrocardiogram (ECG)**

The following ECG measurements will be taken at the time points specified in the Schedule of Events (refer to the Protocol):

- Heart Rate (beats/min)
- PP Interval (msec)
- RR Interval (msec)
- QRS Interval (msec)
- QT Interval (msec)
- QTcB Interval (msec)
- QTcF Interval (msec)

All ECG data collected at scheduled and unscheduled visits will be included in the listings, but only results collected as scheduled visits/time points will be included in the summary tables.

The parameter names that will be used in the outputs will comprise of the test name and the unit of measure, for example, 'Heart Rate (beats/min)'. Parameters will be sorted in the order that the measurements were transferred from the external vendor [REDACTED] within the tables and listings.

ECG measurements will present summary statistics for the results at the baseline and each scheduled post-baseline visit for each of the parameters. In addition, summaries will be presented for the change from baseline values at each scheduled post-baseline visit/time points (continuous descriptive analysis).

Summary of the number and percentage of subjects with average QTcF intervals (< 450ms, 450 – 480 ms, 481 – 500 ms, >= 501 ms) by visit/time point will be provided, as well as summary of the number and percentage of subjects with specific increases from baseline in QTcF intervals (<= 30 ms, > 30 ms, or > 60 ms) by visit/time point.

Since triplicate tracings are done as part of one assessment, the mean of the three tracings per parameter will be summarized for each subject. All values will be listed including the mean value per parameter. Changes from baseline will be calculated based on the mean values of the triplicates where appropriate.

The decimal precision for each parameter will be based on the maximum number of decimals to which the results were reported on the eCRF.

[REDACTED]

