### **13.7 ECOG Performance Status**

ECOG performance status results will be presented in the by-subject data listings. A shift table will be generated using the worst (highest) grade until ED/EOT versus baseline ECOG performance status.

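### No visible QTcF table counts each subject once at the worst post-baseline value, and post-baseline repeat and unscheduled ECGs are listed but not tabulated (minor)

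*SAP*

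**What the plan says.** **Measured QTcF.** SAP 13.4 plans descriptive statistics by scheduled visit and two categorical summaries. The first counts subjects by "average QTcF intervals (< 450ms, 450 – 480 ms, 481 – 500 ms, >= 501 ms) by visit/time point". The second counts increases from baseline (up to 30, above 30, above 60 ms), again per visit or time point. All ECG data are listed, "but only results collected as scheduled visits/time points will be included in the summary tables".

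**Repeats.** SAP 3.1 adds: "If a repeat assessment was performed, the result from the original assessment will be presented as the result at the specific visit/time point". SAP 3.2 makes one exception: repeat and unscheduled assessments before the first dose can supply the baseline value.

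**When repeats occur.** Protocol Table 7.3:1, footnote h: "Any subjects with observed QTcF prolongation of potential significance should have the ECG repeated for confirmation".

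**Worst-value tables elsewhere in the SAP.** For laboratory data (SAP 13.2): "A cross-tabulation of the worst grade that observed in planned and unplanned visits until ED/EOT versus the baseline grade will be presented". For performance status (SAP 13.7): "A shift table will be generated using the worst (highest) grade until ED/EOT versus baseline ECOG performance status".

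**The reported-event route.** Under Protocol 9.2.1 an abnormal QTcF result "should be considered an AE if the average QTcF interval is ≥ 450 ms" or if the mean rises by more than 60 ms. Protocol 9.2.2 lists as an event of clinical interest "QTcF interval ≥ 450 ms or a > 60 ms increase from baseline". SAP 13.1 counts a subject once per system organ class and preferred term, and uses the most extreme grade in the severity tables.

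**The concern.** Protocol 3.2 names QTcF prolongation as the only dose-related effect of FLX475 seen in clinical experience. Protocol 3.1.3.2.2 reports one dose-limiting QTc event in each of the 75 mg and 100 mg monotherapy cohorts, both in subjects with confounding factors; 100 mg is the dose used here. How many subjects ever passed 480 or 500 ms is therefore a basic safety question.

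By-visit rows cannot answer it. If one or two subjects appear in a band at several visits, the table does not say whether they are the same people. The ECGs taken because something looked abnormal are also the ones left out of the measured-value tables. A reader who wants the count in milliseconds would have to rebuild it from listings of up to 60 and 30 subjects.

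**Working it through.** The plan states no QTcF rate, so there is no figure of its own to reproduce. The check has three steps.

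**1. Where each ECG goes (visible text)**

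- Scheduled, original, post-baseline: by-visit tables and listings (SAP 13.4).
- Repeat of a scheduled post-baseline ECG: listing only, because the original is shown (SAP 3.1).
- ECG at an unscheduled post-baseline visit: listing only (SAP 3.1, 13.4).
- Repeat or unscheduled ECG before the first dose: can be the baseline (SAP 3.2), so it can affect the increase-from-baseline bands.
- Any ECG meeting the numeric rule: can reach a summary as a reported event (Protocol 9.2.1, 9.2.2; SAP 13.1), but as a graded term and not in ms.

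The visible text has no row for a subject's maximum. The ECG shift table in Protocol 11.4.3 rests on the investigator's clinical-significance rating, not on measured QTcF.

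**2. What by-visit rows can tell**

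If a share p of subjects is in a band at each of k visits, the share ever in it lies between p and min(1, k × p). For 10 subjects with one above 500 ms at each of 6 visits (C1D8 to C3D1), the number ever above is between 1 (10%) and 6 (60%). The by-visit table looks identical in both cases.

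**3. Illustration of size**

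Visits: Protocol Tables 1.2:1 and 9.2:3 give a subject treated through Cycle 4 eight scheduled post-baseline ECG visits to ED/EOT: C1D8, C1D15, C2D1, C2D8, C2D15, C3D1, C4D1 and ED/EOT. Redacted post-dose time points and the initial follow-up ECG are not counted.

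Assumed, not in the documents: a constant share p above 480 ms per visit; normal values with equal within-subject correlation ρ; full attendance.

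Formula, with c = Φ⁻¹(1 − p):

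P(ever) = 1 − ∫ Φ((c − √ρ·z)/√(1 − ρ))^k φ(z) dz, with k = 8.

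| p per visit | ρ = 0.9 | ρ = 0.7 | ρ = 0.5 |
|---|---|---|---|
| 5% | 10.9% | 16.8% | 21.9% |
| 3% | 7.0% | 11.1% | 14.6% |
| 2% | 4.9% | 7.9% | 10.4% |
| 1% | 2.6% | 4.4% | 5.7% |

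On 30 subjects at 5%, each row shows about 30 × 0.05 = 1.5 subjects. The number ever above 480 ms is 30 × 0.1086 = 3.3, 30 × 0.1683 = 5.0 or 30 × 0.2191 = 6.6. Adding the initial follow-up ECG (k = 9) gives 11.2%, 17.7% and 23.3%.

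No figure is put on the excluded repeats. Footnote h gives no trigger in ms, and the documents give no QTcF variance.

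**The case against.** **The table may exist.** SAP 13.4 ends in a redacted block, and the lists of tables, listings and figures (SAP 18 to 20) are blank in this copy. This stands: the point can only be made of the visible text, and the fix must be conditional.

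**The event tables already answer most of it.** The numeric rules apply at any visit, including unscheduled ones, and SAP 13.1 counts each subject once. This stands in large part and is why the point is minor. It is not a full substitute. Those tables depend on events being reported and graded, and they give no values in ms. Under Protocol 9.2.8 sites evaluate ECGs locally in real time, with central analysis later; SAP 13.4 refers to measurements transferred from an external vendor. A measured-value table would check the reports.

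**The protocol asks for nothing more.** Protocol 11.4.3 specifies a worst-grade laboratory table but none for measured QTcF. This also stands. A reader might infer that the SAP drops a required analysis; the documents do not support that. SAP 13.2 and 13.7 show only that the format is already in use.

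**The repeat rule hides little.** A reader might infer that it removes the prolonged values. It does not: when a scheduled ECG prompts the repeat, the prompting value stays in the table. Footnote h also says repeats should be done, not that they must be. What is lost is any repeat higher than its original, and all ECGs at unscheduled visits.

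**The illustration shows only that ever exceeds per visit.** True. It also ignores the withholding and dose reduction that Table 7.3:1 attaches to several QTcF grades, so a constant rate is a simplification.

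**Conclusion.** The point holds as a minor gap in presentation. In the visible text, measured QTcF is summarised only by visit and only from scheduled original ECGs. Post-baseline repeat and unscheduled ECGs are listed but not tabulated, and no measured-value table counts each subject once at the worst value.

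A reader might go further and conclude that QTcF safety data are lost or concealed. The documents do not support that: all values are listed, and prolongation is captured as an adverse event and an event of clinical interest.

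On size, 5% per visit above 480 ms over 8 visits corresponds to roughly 11% to 22% of subjects ever above it, for correlations from 0.9 to 0.5. At 1% per visit the range is 2.6% to 5.7%. Rates, correlations and attendance are all assumed; these are not forecasts for this trial. Confidence is medium, because redacted text may already contain the output.

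**What to change.** Keep the by-visit tables. Unless a redacted output already provides it, add one table with:

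- each subject's maximum post-baseline mean QTcF category, cross-classified by baseline category;
- each subject's maximum increase from baseline;
- both taken over all scheduled, repeat and unscheduled triplicates through the initial follow-up ECG at 30 (+7) days, or shown both to ED/EOT and through follow-up. Stopping at ED/EOT alone would omit a scheduled ECG that falls at or near the end of the 30-day treatment-emergent window;
- the scheduled-only maximum beside it.

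State in SAP 13.4 that this table is an exception to its scheduled-only rule and to the repeat rule in SAP 3.1.

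**Cost.** SAP wording and one table from data already collected; no visit or procedure changes. The statistical downside is that a maximum rises with longer treatment and with repeats prompted by prolongation, so its incidence will usually exceed that in any by-visit row. The scheduled-only column and the retained by-visit tables limit misreading.

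**Optional confirmations.** (a) State that triplicate means are rounded to whole ms before banding, or write the bands as contiguous, so that nothing falls between 480 and 481 or between 500 and 501 ms. The precision rules in SAP 3.1 and 13.4 can already be read as rounding. (b) Confirm that the ECG clinical-significance shift table in Protocol 11.4.3 is still planned, since visible SAP 13.4 does not mention it.

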### **13.5 Physical Examinations**

The following body systems will be assessed at the time points specified in the Schedule of Events (refer to the Protocol):

- Head/Ears/Eyes/Nose/Throat
- Chest (Heart and Lungs)
- Abdomen
- Skin
- Neurological
- Neck
- Limbs
- Other

By-subject data listings will be created for height, weight, BMI, all body system results (Abnormal Not Clinically Significant, Abnormal Clinically Significant) and a description of abnormal CS, if applicable.

### **13.6 Pregnancy Test Results**

All information related to pregnancy testing (urine and serum based) will be presented in the by-subject data listings.

### **13.7 ECOG Performance Status**

ECOG performance status results will be presented in the by-subject data listings. A shift table will be generated using the worst (highest) grade until ED/EOT versus baseline ECOG performance status.

### **13.8 ECHO or MUGA**

ECHO or MUGA results will be presented in the by-subject data listings.

**14. IMMUNOGENICITY**

Not applicable.

---

[REDACTED]

[REDACTED]

[REDACTED]

**15. CHANGES TO THE PLANNED ANALYSIS**

Not applicable.

---

[REDACTED]

[REDACTED]

[REDACTED]

## **16. INTERIM AND FINAL ANALYSIS**

### **16.1 Interim Analyses**

The study is planned initially for 2-stage design for both cohorts but there might be more than 2 stages depending on the results for each cohort. Based on the initial plan with 2-stage design, the interim analysis for each cohort will be performed when the initial 10 subjects of each cohort completes 4 cycles (or 12 weeks; after 2nd response assessment) or withdrawn from the study, whichever occurs first. At this time both efficacy and safety results as well as any available PK and PD data will be reviewed by the IDMC. The number of subjects for the next stage will be determined based on the interim data analysis as well. Study discontinuation due to futility may be recommended by the IDMC to the Sponsor. More details about the decision making based on the interim analysis will be described in charter.

### **16.2 Final Analysis (End of Study)**

The final analysis will be conducted at the time of end of study which was described in the Section 3.2, the clinical database has been locked, and the analysis populations have been approved. As each cohort will enroll target subjects separately and so the analysis will be performed separately for each cohort as well.

The final analysis will be based on the final version of the SAP. Any deviations from the planned analysis will be documented in the CSR.

**17. SOFTWARE**

- SAS® Version 9.4 or higher (SAS Institute, Cary, North Carolina, USA).

**18. TABLES**

Table Number	Table Title	Population

---

Table Number	Table Title	Population

[REDACTED]

Table Number	Table Title	Population

**19. LISTINGS**

Listing Number	Listing Title	Population

[REDACTED]

Listing Number	Listing Title	Population

[REDACTED]

Listing Number	Listing Title	Population

---

**20. FIGURES**

Figure Number	Figure Title	Population

[REDACTED]

